2.1 Purpose of the Analyses

This is a Phase 2 multicenter, randomized, placebo-controlled, double-blind study to examine the safety and immunogenicity of a 2-injection vaccine regimen (Day 0 and 28) with the CHIKV VLP vaccine or PBS placebo in healthy adults. Note, not all analyses for endpoints included in the protocol are detailed in this plan. This statistical analysis plan details the analyses pertaining to the primary and secondary outcomes. The exploratory immunogenicity endpoint of humoral and cellular immune response as measured by NAb, ELISA and other assays at Week 4, 16, 24, 48, and 72 may not be performed. The only immunogenicity data expected is humoral and cellular immune response as measured by NAb at Week 0 and 8 and ELISA at screening. Also, interim analyses included in the protocol are not detailed in this plan, including the analysis of immune responses and CHIKV incidence rates at 6 and 12 months after the study is closed to accrual.

3 STUDY OBJECTIVES AND ENDPOINTS

3.1 Study Objectives

Primary Objective:

- To evaluate the safety and tolerability of VRC-CHKVLP059-00-VP in healthy adults that reside in CHIKV endemic areas when administered intramuscularly by needle and syringe at a dose of 20 mcg compared to placebo.

Secondary Objectives:

- To evaluate the immune response to VRC-CHKVLP059-00-VP by neutralization assay at 4 weeks after the second 20 mcg dose (Study Week 8).

Exploratory Objectives:

- To evaluate humoral and cellular responses to VRC-CHKVLP059-00-VP at additional time points. CHIKV-specific responses will be assessed by antibody assays that include antigen-specific ELISA and neutralization assay.
- To compare incidence rates of CHIKV infection in vaccine and placebo recipients.
- To compare clinical and virus characteristics of infections in vaccine and placebo recipients.

3.2 Endpoints

3.2.1 Primary Endpoints

Safety

Assessment of product safety will include clinical observation and monitoring of hematological and chemical parameters. Reactogenicity will be closely monitored for 7 days after injection and safety evaluated by clinical visits through the study duration of 72 weeks.

The following parameters will be assessed:

- Local reactogenicity signs and symptoms for 7 days after each injection
- Systemic reactogenicity signs and symptoms for 7 days after each injection
- Laboratory measures of safety through 4 weeks after last injection
- Adverse events through 4 weeks after last injection
- Serious adverse events and new chronic medical conditions throughout the study
- CHIKV infection events throughout the study

3.2.2 Secondary Endpoints

Immunogenicity

- Humoral immune response as measured by neutralization antibody (NAb) assay at baseline (Day 0) and at 4 weeks after second injection (Week 8).

3.2.3 Exploratory Endpoints

Immunogenicity

- Humoral responses to VRC-CHKVLP059-00-VP at additional time points assessed by antibody assays that include antigen-specific ELISA and neutralization assay.

Chikungunya Infection Incidence

- Confirmed Chikungunya infections by positive PCR results for CHIKV at the end of the study.
- Cases of illness clinically consistent with Chikungunya infection confirmed or not by a positive PCR at the end of the study.
- Clinical characteristics of infections based on standard of care parameters for CHIKV disease. Virus characteristics of infections measured by signs and symptoms.

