1.1. Chikungunya: Etiology, Disease Course and Epidemiology

CHIKV (genus *Alphavirus*, family *Togaviridae*) is an arthropod-borne viral disease with a positive, 11.8 kilobase (kb) single-stranded RNA genome encoding structural and non-structural proteins [3, 4]. The virus has three distinct clades that share a high percentage of amino acid similarity: West African, Central/East/South African, and Asian genotypes [5-7].

Initial case reports of CHIKV refer to an outbreak in Tanzania in 1952-53 [8, 9] and early outbreaks were geographically limited [10]. Prior to 2013, CHIKV outbreaks were primarily detected in regions of Africa, Asia, Europe, and the Indian and Pacific Oceans. Late in 2013, the first local transmission of CHIKV was reported in the Americas [11-14]. The virus is transmitted through infected mosquitoes, predominantly *Aedes aegypti*, in sylvatic and human-mosquito-human cycles [12, 13]. Genetic mutations in viral genome have enabled virus transmission through a new host, *Aedes albopictus*, altering CHIKV epidemiology and driving outbreaks in new regions [15-17].

CHIKV infection is associated with severe morbidity lasting 1-2 weeks, with symptoms persisting for weeks to months. The incubation period lasts 2-12 days [18]. Acute clinical manifestation involves high fever, rash, gastrointestinal complications, conjunctivitis, headache, arthralgia, nausea, fatigue and myalgia. The hallmark symptom of the infection, debilitating polyarthralgia/arthritis, is present in nearly all cases (>70%) [11, 18, 19]. Onset of alphavirus-associated arthritis begins within 2-5 days after the infecting mosquito bite, coinciding with presence of virus by polymerase chain reaction (PCR) and innate immune responses against circulating virus. The timing and onset of arthritis is not consistent with adaptive immune responses that occur around day 7-14. Persistent arthritis (3-13% of cases) has been associated with pro-inflammatory cytokines and detectable virus in the joint fluid and cells [20-23]. CHIKV-associated mortality is low; the majority of fatal cases occur in older populations with underlying medical conditions [1, 24]. Though atypical, neurological complications including encephalitis and meningoencephalitis have been seen in a growing number of cases [11, 25, 26].

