3. STUDY OBJECTIVES

3.1. Primary Objective:

- To evaluate the safety and tolerability of VRC-CHKVLP059-00-VP in healthy adults that reside in CHIKV endemic areas when administered intramuscularly by needle and syringe at a dose of 20 mcg compared to placebo.

3.2. Secondary Objectives:

- To evaluate the immune response to VRC-CHKVLP059-00-VP by neutralization assay at 4 weeks after the second 20 mcg dose (Study Week 8).

3.3. Exploratory Objectives:

- To evaluate humoral and cellular responses to VRC-CHKVLP059-00-VP at additional time points. CHIKV-specific responses will be assessed by antibody assays that include antigen-specific ELISA and neutralization assay.
- To compare incidence rates of CHIKV infection in vaccine and placebo recipients.
- Clinical and virus characteristics of infections will also be compared in vaccine and placebo recipients.

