6.2.2. Immunogenicity

The principle immunogenicity endpoints are measured at Week 0 and 8 by neutralization assay. Exploratory immunogenicity endpoints are measured at Week 4, 16, 24, 48, and 72 by neutralization assay, ELISA, and other exploratory research tests.

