6.3. Sample Size and Accrual

The study design is to enroll 400 healthy adult participants ages 18 to 60 that reside in CHIKV endemic areas. Randomization will equally allocate subjects to vaccine or placebo schedules with stratification by ages 18-40 and 41-60 years. The enrollment plan does not include provision for replacing subjects with incomplete injections or visit schedules.

Enrollments may occur rapidly at more than one site. The data management CRO will carefully monitor study enrollment and notify all sites and the VRC Protocol Chair when the completion of enrollment is near.

The sample size for this study was not selected to test a formal null hypothesis. It reflects the number of vaccine doses that are available for the study and the desire to gain maximal information for the conduct of possible Phase 3 follow on trials. This latter consideration is particularly important as reliable estimates of CHIKV incidence in the target population, vaccine effects and logistical considerations in implementing future trials must be understood prior to a Phase III trial. Nevertheless, power computations are provided below as an indication of the probability of observing results of interest.

There are not good data to estimate the loss to follow-up rate for this study. The power calculations assume a 10% loss in both groups for the primary and secondary endpoints. Loss to follow-up for the exploratory outcomes are likely to be larger but are not included as power calculations are not included for these outcomes.

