4.6.3 Chikungunya Infection Incidence

The primary variable for this analysis is PCR-confirmed CHIKV illness. Reports of clinical illness with or without PCR confirmation will also be provided. Throughout the study if a subject reports signs and symptoms of CHIKV infection, blood samples should be collected for diagnostic testing by virus detection (e.g., PCR) by the Primary Diagnostic Laboratory (PDL). This may occur during a scheduled study visit or unscheduled visits may be conducted to complete the testing needed. CHIKV cases will be recorded through the last study visit. Laboratory confirmed cases of CHIKV will be recorded on a CHIKV endpoints form rather than on an AE form without an attribution assessment.

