7 STUDY SUBJECTS

7.1 Subject Disposition

Table 14.1.1 (Appendix I), will present a summary of the reasons that subjects were screened but not enrolled.

The composition of analysis populations, including reasons for subject exclusion, by treatment arm, is presented in **Table 14.1.2, Appendix I**.

The disposition of subjects in the study will be tabulated by site and treatment group (**Table 14.1.3, Appendix I**). The table shows the total number of subjects screened, enrolled, receiving at least 1 dose, receiving at least 2 doses, discontinued dosing or terminated from study follow-up and the number completing the study. CHIKV infection status and subject disposition will be tabulated by site and treatment group (**Table 14.1.4, Appendix I**). The table shows the number and percentages of subjects who had a PCR-confirmed CHIKV infection, those with a clinical CHIKV infection (both further split by when infection occurred), and those uninfected.

A flowchart showing the disposition of study subjects, adapted from the CONSORT Statement [3] will be included (**Figure 14.1.1, Appendix II**). This figure will present the number of subjects screened, enrolled, lost to follow-up, and analyzed, by treatment arm where applicable.

A listing of subjects who discontinued dosing or terminated from study follow-up and the reason will be included in **Listing 16.2.1 (Appendix III)**.

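### Both chikungunya case definitions start from symptoms, so the infection analyses estimate symptomatic illness, and silent infections are counted as uninfected

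*Combined protocol and SAP*

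**What the plan says.** **Objective and purpose.** Protocol 3.3 and SAP 3.1 set the exploratory objective: "To compare incidence rates of CHIKV infection in vaccine and placebo recipients". Protocol 6.3 explains why it matters for Phase 3: "reliable estimates of CHIKV incidence in the target population, vaccine effects and logistical considerations in implementing future trials must be understood".

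**Case definitions.** SAP 3.2.3 lists "Confirmed Chikungunya infections by positive PCR results for CHIKV at the end of the study" and, separately, illness clinically consistent with CHIKV whether or not PCR is positive. SAP 10 gives each definition its own incidence tables, Cox VE and Kaplan-Meier curves.

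**Case finding.** Protocol 4.3.1 and SAP 4.6.3 share one trigger: "Throughout the study if a subject reports signs and symptoms of CHIKV infection, blood samples should be collected for diagnostic testing by virus detection". Footnote 9 of the Schedule of Evaluations (protocol Appendix III) also makes diagnostic sampling conditional on signs or symptoms. Unscheduled visits for testing are allowed. No routine PCR of symptom-free subjects is described.

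**Non-cases.** SAP 7.1 says that Table 14.1.4 will show the PCR-confirmed, "those with a clinical CHIKV infection (both further split by when infection occurred), and those uninfected". SAP 10.2 censors subjects without infection at completion or early termination.

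**Serology.** Protocol 6.2.2 states: "Exploratory immunogenicity endpoints are measured at Week 4, 16, 24, 48, and 72 by neutralization assay". SAP 2.1 expects NAb only at Weeks 0 and 8, and ELISA only at screening.

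**Labels.** SAP 4.6.3 names its primary variable as PCR-confirmed CHIKV *illness*. The VE tables (15.2.x, 15.3.x) and Figures 15.1.x call the same outcome *infection*.

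**The concern.** A subject becomes a case only through symptoms that are reported or seen. An infection that causes none, or none that the subject ever mentions, cannot enter either definition. That subject then appears in the disposition table as uninfected and in the time-to-event analysis as infection-free to the end of follow-up.

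Two readings are at stake. A Phase 3 planner who takes the incidence figures as infection attack rates will plan on rates that leave out silent infections. A reader of the VE tables may take protection against illness for protection against infection. The two coincide only if the silent share is the same in both arms.

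**Working it through.** The plan states no figure that depends on case finding, and protocol 6.3 gives no power for these outcomes, so there is nothing to reproduce. The check has four parts. Silent share, PCR window, sampling share and attack rate are assumptions.

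**1. How often a scheduled visit falls in the PCR window.** From the protocol schedule, visits fall on Days 0, 28, 56 and then every 56 days to Day 504. The gaps are 28, 28 and 8 × 56 days, so 8-week gaps cover 448/504 = 89% of follow-up. If infections are spread evenly and PCR stays positive for *d* days (*d* no longer than 28), the share with a scheduled visit inside the window is 10*d*/504:

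| Assumed window | Share |
|---|---|
| 5 days | 50/504 = 9.9% |
| 7 days | 70/504 = 13.9% |
| 10 days | 100/504 = 19.8% |
| 14 days | 140/504 = 27.8% |

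PCR confirmation therefore rests mainly on self-report and unscheduled visits.

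**2. Capture.** Let *s* be the silent share and *r* the share of symptomatic infections sampled in time.
- PCR endpoint: (1 − *s*) × *r*. With *s* = 5–30% and *r* = 50–100%, the range is 0.70 × 0.50 = 35% to 0.95 × 1.00 = 95%.
- Clinical endpoint: at most 1 − *s*, so 70–95%. This requires every symptomatic infection to be reported and to meet the definition.
- Silent infections: 0% under either endpoint.

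Example: 10 infections among 200 subjects, *s* = 15%, *r* = 80%. PCR finds 10 × 0.85 × 0.80 = 6.8, the clinical definition finds up to 8.5, and 1.5 are never found.

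**3. Effect on VE.** With equal sampling in both arms, observed VE = 1 − RR × (1 − *s*_vaccine)/(1 − *s*_placebo), where RR is the risk ratio for infection.
- Equal silent shares: a true 50% stays 50%.
- 15% silent in placebo and 50% in vaccine: a true 50% appears as 1 − 0.5 × 0.50/0.85 = 71%, and a true 0% as 1 − 0.50/0.85 = 41%.

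**4. What planned serology could add.** Placebo recipients have no vaccine-induced antibody, so a rise in NAb points to infection. The planned Week 8 placebo response rate (SAP 3.3, Table 14.2.1) counts any titer of 30 or more, whatever the baseline. SAP 9 reports positive Week 0 results at some sites, so that rate mixes past with new infection. Restricting to Day 0 titers below 30 and requiring a 4-fold rise separates them. Values below detection are set to 15, so the Week 8 titer must reach at least 4 × 15 = 60. The interval is 56/504 = 11% of follow-up. Infections just before Week 8 may not yet show, since protocol 1.1 puts adaptive responses at about day 7–14.

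**The case against.** The strongest reply is that the SAP does not depend on PCR alone. Medical history is taken at every visit, so an illness first mentioned weeks later can still be a clinical case, and clinical cases are dated by symptom onset (SAP 10.2). Unscheduled visits can be made at any time. SAP 4.6.3 already says *illness*, and the VE table titles carry the qualifiers *clinical* or *PCR confirmed*. Protocol 4.3.1 also refers to a case-identification plan that is not among these documents. The incidence and VE analyses are exploratory, unpowered and, under protocol 6.4.4, without an order of primacy.

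Most of this stands, and it rules out three inferences a reader might draw.
- *Infection is found only by PCR, and late-reported illness is counted as uninfected.* The clinical endpoint and its separate block in Table 14.1.4 contradict this.
- *The incidence objective goes unanswered.* It is answered for symptomatic illness.
- *A definite share of infections is lost.* The documents do not say how long PCR stays positive; the timing statement in protocol 1.1 concerns arthritis and adaptive immunity.

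The reply does not remove the core. The clinical definition also needs symptoms. It has no symptom criteria in these documents, so it may take in other illnesses as well. Placebo NAb results will be reported, but they are neither conditioned on baseline nor linked to infection status.

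**Conclusion.** The point holds in limited form. The exploratory analyses estimate the incidence of, and efficacy against, symptomatic CHIKV illness. Silent or never-reported infections are counted as uninfected and censored as infection-free. True infections are therefore under-counted, by an amount the documents do not allow to be calculated; the 35–95% PCR capture is an illustration under assumed inputs.

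A reader might also infer that VE is inflated. The documents do not support that as a general statement. The bias against infection arises only if vaccination makes infections more often silent, and nothing in the documents shows that it does. VE against symptomatic illness does not have this bias.

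The Week 8 NAb conclusion is unaffected. SAP 3.2.1 lists CHIKV infection events among the safety parameters, but the incidence and efficacy analyses sit in SAP 10 and are labelled exploratory. The change is worth making because it is cheap and settles what the tables may conclude.

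**What to change.** 1. **Wording.** In SAP 3.2.3, 7.1, Table 14.1.4 and Tables and Figures 15.x, extend the SAP 4.6.3 term: *PCR-confirmed CHIKV illness* and *clinical CHIKV illness*. Replace *uninfected* with *no CHIKV illness detected*. State VE as efficacy against symptomatic illness. Cite the case-identification plan named in protocol 4.3.1. Cost: text only.

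2. **One table from planned data.** Among placebo recipients with a Day 0 NAb titer below 30 and a Week 8 result, report the proportion with at least a 4-fold rise at Week 8, overall and by site, with an exact 95% CI. Place it beside the PCR and clinical counts for the same subjects. List baseline-positive placebo subjects separately. Cost: one table, no new assays.

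3. **Optional.** If the Week 72 NAb in protocol 6.2.2 is run, report the same placebo seroconversion from Day 0 to Week 72. With the protocol's assumed 10% loss, this is about 200 × 0.9 = 180 assays on serum the schedule already collects. SAP 2.1 says these assays may not be performed, so this should not be a condition for the first two changes.

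Limit: the serological figure covers placebo only, and only the first 8 weeks unless change 3 is made. It informs incidence and not VE.

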3.3 Study Definitions and Derived Variables

The baseline value will be defined as the last value obtained prior to the first injection of study product on Day 0.

Individual neutralization antibody (NAb) assay results will be reported as a titer. The lower limit of detection for the NAb assay is 15 reciprocal serum dilution and the lower limit of confidence is 30 reciprocal serum dilution. Values below the limit of detection will be imputed as 15 if not already imputed prior to analysis. For analysis, the arithmetic mean of repeated results for each sample will be computed and used as the response for all subsequent calculations.

Fold-rise (NAb) is a measure that describes how much the NAb titer changes from an initial to a final value. The fold-rise is calculated as the ratio of the final value to the initial value.

Positive response rate (NAb) will be measured as the proportion of subjects with a positive response, defined as a reciprocal serum dilution ≥ 30 .

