5.2 Power Calculations for Evaluation of Immune Responses

A secondary objective is to evaluate the humoral immunogenicity of VRC-CHKVLP059-00-VP by neutralization assay at 4 weeks after the second 20 mcg dose (Week 8). Vaccine specific neutralization antibodies are not anticipated in the non-vaccinated group. Therefore, direct comparison between the active and placebo group is of minimal value in assessing sample size. Preliminary Phase 1 neutralization data suggest that neutralization results at the visit with peak response are log-normally distributed with a mean and standard deviation on the log-scale of 7.41 and 0.67 respectively. This standard deviation is rounded up to 0.70 and two more conservative options of 1.0 and 1.5 result in 95% confidence intervals (CI) for geometric mean titers (GMT) (Table).

Table 4: 95% CI for GMT Neutralization among Vaccinees at Time of Peak Response (n=180 per Group)

Assume Standard Deviation on Log Scale	95% CI for GMT Neutralization Among Vaccinees (n=180) at Time of Peak Response
0.70	(1490.7, 1831.7)
1.0	(1426.6, 1914.1)
1.5	(1324.8, 2061.1)

The study is not designed to compare two groups defined by baseline covariates such as gender or age strata. However, the following table is included to provide a sense of the power available for such comparisons. The simple case of two groups (e.g., male and female), assuming equal participation (i.e., 90 subjects for each gender-vaccine group), is given in Table for comparing response rates.

Table 5: Detectable Geometric Mean Ratio between Two Groups for Power = 80% or 90% Assuming Type I Two-Tail Error Rate of 5% (n=90 per Group)

Power	Standard Deviation on Log Scale	Detectable Geometric Mean Ratio (n=90 per group)
80%	0.7	1.34
	1.0	1.52
	1.5	1.88
90%	0.7	1.40
	1.0	1.63
	1.5	2.08

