9 IMMUNOGENICITY EVALUATION

Specimens to evaluate immunogenicity will be taken at baseline and at specified time points. The primary immunogenicity timepoint is 4 weeks after the second injection. Measurements of CHIKV-specific humoral immune responses will be assessed by neutralization antibody (NAb) assays. A listing of individual titer levels and the corresponding planned and actual collection dates are presented in **Appendix III, Listing 16.2.6**.

At some sites, positive baseline Week 0 neutralization antibody assay results were reported. ELISA response data, captured as part of the screening eligibility process, have been received by the Sponsor from the laboratory. When raw ELISA data is received, baseline ELISA responses will be assessed in relation to neutralization antibody data and results will be reported. For further information, a separate analysis plan will be created to elaborate on specific analyses to be performed.

The principle immunogenicity endpoint is measured at Week 8 by neutralization assay.

Descriptive analyses will be presented by study day, age group, and treatment group, aggregated over all study sites and by site. If none or a very small number of placebo group subjects have a neutralization response, their results will only be reported for the positive response rate summaries and omitted from other analyses. This approach is taken to achieve brevity and easier understanding of results when the control group has no meaningful responses.

Summaries include:

- GMT and their confidence intervals (**Table 14.2.1, Appendix I**)
- Geometric mean ratio (GMR) of results obtained at baseline (Week 0) to results obtained at Week 8 and its 95% CI. (**Table 14.2.1, Appendix I**)
- Positive response rates, as defined by an assay-specific post dose response, and their exact 95% CI (**Table 14.2.1, Appendix I**)
- Reverse cumulative distribution of the neutralization assay results (**Figure 14.2.1, Appendix II**)
- Boxplots of titer values (**Figure 14.2.2, Appendix II**).

These summaries will be repeated for all exploratory research tests used to measure exploratory immunogenicity endpoints at the timepoints for which there are data.

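### SAP 3.3 averages repeated neutralisation titres arithmetically, which does not fit the GMT and GMR summaries and shifts them slightly upward

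*Combined protocol and SAP*

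**What the plan says.** SAP 3.3 sets the rule for the NAb assay: "the arithmetic mean of repeated results for each sample will be computed and used as the response for all subsequent calculations". The sentence before it deals with low values: "Values below the limit of detection will be imputed as 15 if not already imputed prior to analysis". The assay limits are given as follows: "The lower limit of detection for the NAb assay is 15 reciprocal serum dilution and the lower limit of confidence is 30 reciprocal serum dilution". A positive response is "defined as a reciprocal serum dilution ≥ 30", and fold-rise is the final titre divided by the initial one.

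SAP 5.2 plans precision on the basis that "neutralization results at the visit with peak response are log-normally distributed", with log mean 7.41 and log SD 0.67.

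SAP 9 lists five summaries:
- "GMT and their confidence intervals"
- "Geometric mean ratio (GMR) of results obtained at baseline (Week 0) to results obtained at Week 8 and its 95% CI"
- the positive response rate with an exact interval
- the reverse cumulative distribution
- boxplots of titres

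Table 14.2.1 in SAP Appendix I adds p-values for GMT, GMR and response rate. The SAP gives no reason for the arithmetic mean, no number of replicates, no replicate variability and no sensitivity analysis with geometric averaging.

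**The concern.** The GMT and GMR are multiplicative summaries, obtained by averaging logs and back-transforming. Averaging replicates on the raw scale first and then taking logs across subjects mixes two scales. The arithmetic mean of positive numbers is never below their geometric mean, and the two are equal only when the replicates agree. The discrepancy therefore goes one way, does not shrink as subjects are added, and is not reflected in the confidence interval.

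Week 8 NAb is the secondary endpoint (SAP 3.2.2). The same averaged value is also compared with 30. That matters for two questions raised in SAP 9: positive Week 0 results have already been seen at some sites, and the number of placebo responders decides whether placebo results are dropped from the other summaries.

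**Working it through.** **Inputs from the documents.** Log mean 7.41, planning log SDs 0.70, 1.0 and 1.5, and n = 180 (SAP 5.2); floor 15 and cut-off 30 (SAP 3.3).

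**Inputs assumed.** k = 2 or 3 replicates per sample, log-normal replicate error, and natural-log SD s between 0.2 and 0.5. The documents give none of these; SAP 3.3 speaks only of "repeated results for each sample".

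**Step 1: the plan's own interval.** exp(7.41) ≈ 1652. The interval is exp(7.41 ± t × SD/√180), with t the 97.5% point on 179 degrees of freedom.

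| Log SD | Recomputed | SAP Table 4 | Upper half-width (stated limit/1652 − 1) |
|---|---|---|---|
| 0.70 | 1490.8 to 1831.6 | 1490.7 to 1831.7 | 11% |
| 1.0 | 1426.4 to 1914.3 | 1426.6 to 1914.1 | 16% |
| 1.5 | 1325.3 to 2060.3 | 1324.8 to 2061.1 | 25% |

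The table reproduces and is not in dispute. It serves as the yardstick.

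**Step 2: a single pair of replicates.** For duplicates r-fold apart, arithmetic mean/geometric mean = (1 + r)/(2√r). This gives 1.02 at r = 1.5, 3/(2√2) = 1.06 at r = 2, 1.15 at r = 3, and 5/4 = 1.25 at r = 4. No distributional assumption is needed.

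**Step 3: inflation of the GMT.** The approximate factor is exp(s²(1 − 1/k)/2). For k = 2 and s = 0.3 this is exp(0.09/4) = 1.023. Simulation of 1,000,000 samples gives:

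| s | k = 2 | k = 3 |
|---|---|---|
| 0.2 | 1.010 | 1.013 |
| 0.3 | 1.022 | 1.030 |
| 0.5 | 1.061 | 1.084 |

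At the planning GMT of about 1652 with duplicates, the reported GMT becomes about 1669, 1690 and 1753. Under geometric averaging the factor is 1.00 by construction.

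**Step 4: the ratio to baseline.** If all baseline replicates are at 15, the baseline value is 15 under either rule and the Week 8/baseline ratio carries the whole Week 8 factor. If baseline is measurable with similar scatter, the two factors largely cancel. SAP 9 words the GMR as baseline to Week 8; formed that way round, the same factor appears inverted.

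**Step 5: the cut-off.** Duplicates of 15 (floored) and 45 have arithmetic mean (15 + 45)/2 = 30, positive, but geometric mean √(15 × 45) = 26.0, negative. Duplicates of 20 and 40 give 30 against 28.3. No simulated sample moved from positive to negative. For underlying titres of 25 to 30, the arithmetic rule adds this much to the chance of a positive call:

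| s, with k = 2 | Added chance (percentage points) |
|---|---|
| 0.2 | about 1 to 3 |
| 0.3 | 3 to 4 |
| 0.5 | about 6 |

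With three replicates at s = 0.5 it is about 10 points.

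**Step 6: vaccinees at planned titres.** With 2,000,000 simulated vaccinees and duplicates at s = 0.5, the response rate is 100% under both rules at log SD 0.70. At log SD 1.5 it is 99.58% (arithmetic) against 99.54% (geometric), a difference below 0.1 point.

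**The case against.** The case for leaving the rule alone has several parts.

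- **Size unknown.** The SAP's wording could mean routine replicates or occasional re-runs. If most samples have one result, the rule hardly matters. This stands: the figures above are conditional on the assumptions.
- **Different level of variation.** The log-normal statement in SAP 5.2 describes titres across subjects, not error within a sample. This also stands. It weakens the simulated figures, but not the mismatch with GMT and GMR or the pairwise ratios in step 2.
- **Very noisy replicates are implausible.** A replicate SD of 0.7 would give about 12% with duplicates, above the narrowest half-width. But its variance is 0.49, more than the total of 0.67² = 0.449 if the Phase 1 values were single results. If they were duplicate means, 0.245/0.449, about 55% of all variation, would be assay noise. That case should not be relied on.
- **Nothing turns on it.** The study tests no formal hypothesis (SAP 6.8), the documents state no success threshold for GMT or response rate, and both arms follow the same rule with the laboratory blinded. This limits the severity.
- **Baseline positives have their own route.** SAP 9 will compare them with screening ELISA under a separate plan. That plan would still start from calls made with the arithmetic rule.
- **The remedy is partial.** Under geometric averaging, 15 and 60 still give √900 = 30. One noisy replicate counts for less but still counts.

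A reader might also infer that every NAb summary is on the log scale. SAP 9 does not support this: only GMT and GMR necessarily are, the response rate is a threshold summary, and no scale is stated for the curves or boxplots.

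**Conclusion.** The rule is inconsistent with the GMT and GMR summaries and with the planning model, and relative to log-scale averaging its effect on the GMT is upward only. Its size is not established. On the assumption of duplicates with natural-log SD 0.2 to 0.5, it is about 1% to 6%, inside even the narrowest planned half-width of about 11%. The ratio to baseline carries this in full only where baseline is at the floor.

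It would be tempting to conclude that both secondary-endpoint summaries, GMT and response rate, are materially biased. The documents do not support that. They contain no replicate data from which to show a material GMT bias, and the vaccinee response rate at planned titres moves by less than 0.1 point. The cut-off effect is confined to discordant samples near 30, which in practice means baseline, placebo and low responders.

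This is a minor point and a nearly free improvement.

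**What to change.** In SAP 3.3, replace the arithmetic mean with the geometric mean of the repeated results (mean of the log titres, back-transformed), taken after values below 15 are set to 15. Use that single value for GMT, GMR, fold-rise and the cut-off of 30. State how many replicates each sample has. If the arithmetic rule is kept, give the reason and add a sensitivity analysis with geometric averaging.

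The cost is one line of SAP text and one line of code. Reported GMTs become slightly lower, and a few borderline samples may change from positive to negative.
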